3.0	03/06/21	Clarification to recruitment target, amendment to inclusion/exclusion criteria
3.1	10/09/21	TBM Sample Recruitment period updated
4.1	01/10/21	Extend recruitment target, recruitment period, follow-up duration, and molecular analysis
4.2	18/03/22	Updated sample shipment details

2 Table of acronyms

Acronym	Meaning
CCR	Committee for clinical research
CH	Conventional histology
CRF	Case report form
CT	Computed tomography
CUP	Cancer of unknown primary
EBV	Epstein Barr virus
FNAC	Fine needle aspiration cytology
GCP	Good clinical practice
H&E	Haematoxylin and eosin stain
H&N	Head and neck
HNC	Head and neck cancer
HNSCCUP	Head and neck squamous cell carcinoma of unknown primary
HPV	Human papilloma virus
ICF	Informed consent form
IRAS	Integrated research application system
MDADI	M. D. Anderson Dysphagia Inventory
MDT	Multidisciplinary team
MRI	Magnetic resonance imaging
MTA	Material Transfer Agreement (Part of HRA Statement of Activities)
PET CT	Positron emission tomography and computed tomography
PIS	Participant information sheet
REC	Research ethics committee
RMH	Royal Marsden Hospital
RVI	Royal Victoria Infirmary, Newcastle (laboratories)
SAE	Stamped addressed envelope
SCC	Squamous cell carcinoma
SOP	Standard operating protocol
SSS	Step serial sectioning
TBM	Tongue base mucosectomy

3 Project summary

Study title	Evaluation of the role of tongue base MucOsectomy and Step serial Sectioning in the management of the unknown primary squamous cell cancer in the head and neck.
Short title	The MOSES Study.
Study design	Multicentre prospective observational cohort study, incorporating histopathological and molecular tissue analysis.
Study setting	UK centres performing TBM for suspected HNSCCUP.
Study participants	Patients with suspected head and neck squamous cell carcinoma of unknown primary (HNSCCUP) undergoing tongue base mucosectomy (TBM).
Planned sample size	100.
Follow-up duration	5 years.
Planned study period	Until recruitment of planned sample size.
Aim	To understand the current management of suspected HNSCCUP patients undergoing TBM in the UK, including adequacy of current histology, functional and oncological outcomes, and disease biology.
Objectives	
Primary:
 
 To establish if step serial sectioning (SSS), compared to conventional histology, improves identification of a primary site in TBM and tonsil specimens in suspected HNSCCUP. 
Secondary:
 
 To compare the pick-up rate of primary cancers in TBM specimens between surgical methods (robotic vs laser vs endoscopic). To prospectively evaluate swallowing function and pain scores after TBM. To understand patient views and experiences of undergoing TBM for suspected HNSCCUP. To report time-to-event data for local, regional and distant disease recurrence, and mortality. To assess the molecular makeup of patients with suspected HNSCCUP undergoing TBM.
Methods	
 Identification of patients prior to TBM surgery. Step serial sectioning histology performed on tongue base and tonsil tissue (if available) to compare to conventional histology results. Functional follow-up using patient completed questionnaires for pain and swallowing function (MDADI) at baseline and intervals up to 5 years. Clinical oncological follow-up recorded for up to 5 years. Exploratory molecular analysis of tongue base, tonsil (if available) and cervical metastatic tissues.
Expected outcomes	
 Increased identification of single and multi-focal primary cancers on SSS. Reasonable recovery of functional outcomes after TBM surgery prior to administration of radiation therapy. Acceptance of TBM and SSS amongst suspected HNSCCUP patients. Greater understanding of the molecular make-up of suspected HNSCCUP.

4 Signature page

The undersigned confirm that the following protocol has been agreed and accepted and that the Chief Investigator agrees to conduct the study in compliance with the approved protocol and will adhere to the principles outlined in the Declaration of Helsinki, the Sponsor's SOPs, and other regulatory requirement.

I agree to ensure that the confidential information contained in this document will not be used for any other purpose other than the evaluation or conduct of the investigation without the prior written consent of the Sponsor

Human papilloma virus (HPV) is thought to play a significant role in many of these cancers presenting as CUP.[6,7] Smaller or involved primary foci are known to be more common in HPV related cancers which may be contributing to the apparent incidence of these unknown primaries, or occultomas as they may also be called. A histological technique called step serial sectioning (SSS) allows examination of tissue specimens in greater detail than conventional histology. It has not previously been used to investigate the primary site in head and neck cancer but the oropharyngeal tissues that potentially harbour these small primaries make a sensible target to pioneer its usage. It is hypothesised that utilising SSS on tonsillectomy and TBM specimens may increase the identification rate of the primary site and may subsequently affect recommended management.

Currently, we do not understand why some cancers present with cervical metastases with no evident primary site. There has been an explosion in genomics research in many cancers, but this remains an understudied area in head and neck cancer. There are currently no treatments available to patients with head and neck cancer based on genomic insights. This study aims to begin to address the unmet need of patients who present with these poorly understood cancers and to provide a starting point for more detailed investigations into the relationships between cancer genomics and clinical outcomes.

6 Study aim and objectives

6.1 Aim:

To understand the current management of suspected HNSCCUP patients undergoing TBM in the UK, including adequacy of current histology, functional and oncological outcomes, and disease biology.

6.2 Primary objective:

- To establish if step serial sectioning (SSS), compared to conventional histology, improves identification of a primary site in TBM and tonsil specimens in suspected HNSCCUP.

6.3 Secondary objectives:

1. To compare the pick-up rate of primary cancers in TBM specimens between surgical methods (robotic vs laser vs endoscopic).
2. To prospectively evaluate swallowing function and pain scores after TBM.
3. To understand patient views and experiences of undergoing TBM for suspected HNSCCUP.
4. To report time-to-event data for local, regional and distant disease recurrence, and mortality.
5. To assess the molecular makeup of patients with suspected HNSCCUP undergoing TBM.

7 Study design and setting

7.1 Study design

Multicentre prospective observational cohort study, incorporating histopathological and molecular tissue analysis.

[Qualitative descriptive study with thematic analysis].

7.2 Study setting

UK centres performing TBM to for suspected HNSCCUP.

8 Patient eligibility criteria

8.1 Population

Suspected HNSCCUP patients, with a diagnosis of squamous cell cancer from cervical lymph node biopsy, with the primary disease presumed to be of head and neck origin, who have not had the primary site identified by either clinical examination or cross-sectional imaging (CT/MRI) including PET CT.

8.2 Inclusion criteria

- Aged 16 or over
- Both sexes
- Cervical metastatic SCC, confirmed with cytology or biopsy, undergoing TBM for identification of primary site

8.3 Exclusion criteria

- Primary site identified by any means prior to being indicated for TBM
- Patients undergoing targeted biopsies or resections
- Patients known to have a history of previous H&N cancers
- Patients known to have undergone previous radiation to the H&N region

9 Study procedure and methodology

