9.7 Handling of tissue specimens and histological processing

All tissue will undergo conventional histological processing at the local site and will be used to influence patient management by the local team according to local practices. The following tissues will then be requested to be sent by the local teams to RMH for further analysis:

- Oropharyngeal tissues from diagnostic surgeries attempting to identify the primary site (i.e., TBM specimens, and tonsils, if available)
- Cervical nodal specimens, from the diagnostic neck biopsies (fine needle aspiration cytology and/or core biopsies) and/or therapeutic neck surgeries, if available
- A buccal swab and/or blood sample (for germline DNA)

Where SSS is indicated (TBM and tonsil specimens, if available) the MOSES team will then send these tissues onto the RVI. Appropriate tissue handling practices will be observed. RMH uses FreezerPro Laboratory Management Software to facilitate handling and tracking of tissue specimens.

Anonymised histopathology reports will be requested from local centres. The macroscopic description will be used to orientate the submitted tissue blocks undergoing step serial sectioning.

Step serial sectioning

The paraffin blocks supplied from TBM and tonsil specimens will undergo step serial sectioning using the following method:

- Steps every 0.5mm with five serial 4 μ m sections taken.
- Each block will be processed in this way until the material is consumed.
- Slides will be stained with haematoxylin and eosin stain (H&E) and examined for signs of SCC.
- If an SCC is identified, then serial sections 2 and 4 will be submitted for HPV testing (p16 immunohistochemistry and high-risk HPV DNA in situ hybridisation).
- Serial sections 1 and 5 will be retained for repeat tests if required.
- The pathologist will compose a report and complete the relevant sections of the CRF.
- Unused material will be returned to the contributing centres if desired. Some material may be retained for further study, as detailed in the PIS and ICF.

Exploratory molecular analysis

Patients will be asked to provide buccal swabs and/or blood samples for germline DNA analysis. These samples may be provided at any time point following recruitment.

Packaging and sending

All MOSES blood and/or buccal swab samples should be collected, labelled, stored and shipped as detailed in the **MOSES Sample Collection Manual**.

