12.1 Sample size

No a prior sample size calculation was performed as initial funding limited recruitment to analysis of 60 specimens to undergo SSS. Meta-analysis shows a pickup rate of 58% for this cohort. We anticipate a potential increase pick up rate of around 10%.

- With 60 specimens, the 95% confidence interval boundaries around the pickup rate are +/- 12.6% for 58% and +/-11.4% for 68%.

In anticipation of further funding, our sample size is increased to 100 to give greater confidence in the effect size.

- With 100 specimens, the 95% confidence interval boundaries around the pickup rate are +/- 9.8% for 58% and +/-9.0% for 68%.

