12.2 Study endpoints

For the Primary objective:

- Identification of cancer in the tonsillectomy or TBM specimen on histology.

For the Secondary objectives:

- To compare the pick-up rate of primary cancers in TBM specimens between surgical methods (robotic vs laser vs endoscopic).
 - Identification of cancer in the tonsillectomy or TBM specimen on histology.
 - We anticipate no significant disparity in pick up rate between methods with the limited number of cases in this study.
- To prospectively evaluate swallowing function and pain scores after TBM.
 - We anticipate no significant change in means from pain and MDADI scores between 0 and 6 week questionnaires. Results at 3 weeks are anticipated to be different as still recovering from surgery. Results up to 60 months will evaluate effects of any subsequent treatments and future recovery.
- To understand patient views and experiences of undergoing TBM for suspected HNSCCUP.
 - Qualitative thematic analysis therefore no quantitative end point.
- To report time-to-event data for local, regional and distant disease recurrence, and mortality.
 - Primary emergence rate of around 3% per year.
- To assess the molecular makeup of patients with suspected HNSCCUP undergoing TBM.
 - (Exploratory analysis)

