12.4 Analysis methods

Descriptive analysis only is anticipated. The rate of CH and SSS pick up will be reported in the overall specimens and separately in the sub-group of surgical methods with 95% confidence intervals. The pain scores and swallow recovery with MDADI scores will be reported using mean/median and standard deviation or range as appropriate at each time point of 0, 3 weeks, 6 weeks, 3 months, 6 months and 12 months, 24 months, 36 months, 48 months and 60 months. Similarly, score change between time points will be summarized in the same way. The primary and secondary analysis will be done when the complete sample size is recruited and last patient on the study completed all follow-ups.

Molecular data analysis

Detailed description of the molecular analysis methodology is beyond the scope of this protocol.

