12.8 Expected Outcomes of the Study

TBM is a relatively new surgical procedure with little data relating to patients experience and recovery from this operation. The pain and MDADI questions will go some way to showing the acceptability of this procedure to patients. It is expected that by 6 weeks the pain and MDADI scores will have returned to near baseline. Most patients will go on to receive radiotherapy to their pharyngeal mucosa, which is known to worsen swallowing function. This data will go some way to clarifying that any subsequent difficulties may not be attributable to the TBM procedure.

Any increased pick up rate resulting from SSS could lead to wider adoption of this process in the management of HNSCCUP. The size of any primary sites identified through SSS over conventional histology will also be recorded and could influence the size of histological levels employed for future TBM and tonsillectomy specimens in the future management of HNSCCUP.

Data from the patient interviews and thematic analysis should help to guide patient goals for any further research in HNSCCUP. Of particular note will be the patients' wishes regarding timing of the tonsillectomy and TBM procedures, which can occur separately, particularly if initial investigation is performed in a peripheral hospital that does not offer TBM. The potential changes in management from identification of primary sites using SSS, and potential for escalation of treatment through the addition of concomitant chemotherapy will also be novel.

Results from the exploratory molecular analysis are expected to give us greater understanding of the molecular make-up of suspected HNSCCUP. Including, but not limited to, how cancers where the primary is identified differ from those primaries that remain occult, and how the cervical disease differs from primary site tissues in the oropharynx.

Results from this prospective observational study will form the foundation of a potential phase III trial investigating the roles of TBM and SSS in management of suspected HNSCCUP. The precise research question is yet to be established.

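### Secondary objective 1 concerns TBM specimens, but its endpoint in 12.2 also counts tonsils; as a lesser point, tonsils reported before TBM was indicated deserve their own row

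*Protocol*

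**What the plan says.** **Secondary objective 1.** Protocol 6.3 (and the summary in section 3) reads "To compare the pick-up rate of primary cancers in TBM specimens between surgical methods (robotic vs laser vs endoscopic". In 12.2 the endpoint listed under this objective is "Identification of cancer in the tonsillectomy or TBM specimen on histology", the same as for the primary objective. The primary objective itself names both TBM and tonsil specimens, so for that objective the endpoint fits.

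**Analysis.** Section 12.4 plans descriptive analysis: "The rate of CH and SSS pick up will be reported in the overall specimens and separately in the sub-group of surgical methods". Each rate is to carry a 95% interval. The section names no split by specimen type or by when the tonsil was removed.

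**Entry of earlier tonsils.** Section 8.3 excludes "Primary site identified by any means prior to being indicated for TBM". Section 12.8 refers to the "timing of the tonsillectomy and TBM procedures, which can occur separately, particularly if initial investigation is performed in a peripheral hospital". Section 9.7 requests "Oropharyngeal tissues from diagnostic surgeries attempting to identify the primary site (i.e., TBM specimens, and tonsils, if available" and sets no limit on timing.

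**Figures.** Section 12.1 says "Meta-analysis shows a pickup rate of 58% for this cohort" and anticipates a gain of around 10%, hence 68%. It does not say whether the 58% refers to TBM alone, or to patients with or without earlier tonsillectomy. The protocol gives no tonsil pick-up rate and no share of patients with earlier tonsils.

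**The concern.** The objective and its endpoint describe different quantities. If 12.2 is followed, a patient whose only cancer lies in a tonsil is a success for the robotic, laser or endoscopic method used on the tongue base. The reported method rates would then partly describe tonsil disease and tonsillectomy practice.

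The second issue concerns the overall rates. A tonsil that was positive on CH before TBM was indicated removes the patient from the study. Every such earlier tonsil that does enter is therefore CH-negative by selection, while SSS may still find cancer in it. A tonsil removed with the TBM can be positive on either. Pooling the two makes the overall CH rate, and the size of the SSS gain, depend partly on the mix. Section 12.8 says an increased pick-up could lead to wider adoption of SSS, so readers need to see what the pooled figure is made of.

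**Working it through.** **1. The plan's own precision figures.** Section 12.1 gives, for 100 specimens, ±9.8 points at 58% and ±9.0 at 68%. Exact (Clopper-Pearson) 95% intervals for 58/100 and 68/100 have upper arms of 9.80 and 8.98, so the figures reproduce as upper arms. These half-widths concern single rates, not the paired difference.

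**2. Set-up (patient level, CH).** Call a patient staged if the tonsils were reported CH-negative before TBM was indicated.
- t = tonsil CH-positive rate, assumed 10-40%.
- b = TBM CH-positive rate given a CH-negative tonsil.
- s = staged share, assumed.
- Unstaged any-site rate = 1-(1-t)(1-b); staged any-site rate = b.
- Reading A takes 58% as the unstaged rate, so b = 1-0.42/(1-t). Reading B takes b = 58%.

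**3. What the tonsil adds to a method's rate.** Assume every patient has tonsil tissue and no disease is multifocal. The unstaged TBM-only rate is then (1-t)b, and counting tonsils adds (1-s)t to a method's rate. With t = 20%, that is 15 points at s = 25% and 5 points at s = 75%. None of it is tongue-base pick-up.

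**4. Does TBM-only remove the effect of staging?** Take two methods with equal TBM performance and assumed staged shares of 25% and 75%. The any-site gap is 0.5·t·(1-b), with the less staged method higher. The TBM-only gap is 0.5·t·b, with the more staged method higher.

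| t | A: b | A: any-site gap | A: TBM-only gap | B: any-site gap | B: TBM-only gap |
|---|---|---|---|---|---|
| 10% | 53.3% | 2.3 | 2.7 | 2.1 | 2.9 |
| 20% | 47.5% | 5.3 | 4.8 | 4.2 | 5.8 |
| 30% | 40.0% | 9.0 | 6.0 | 6.3 | 8.7 |
| 40% | 30.0% | 14.0 | 6.0 | 8.4 | 11.6 |

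The TBM-only gap is the larger whenever b exceeds 50%, which is 5 of these 8 cases. Restriction therefore does not cure staging. Within the staged stratum the TBM rate is b for both methods, and within the unstaged stratum it is (1-t)b, so stratifying does.

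**5. The pooled SSS-minus-CH difference.** Let g be the SSS yield among CH-negative patients, taken from the plan's 58% and 68%: g = 10/42 = 23.8%. Difference = g·(1-CH). At s = 50%:

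| t | A: CH | A: difference | B: CH | B: difference |
|---|---|---|---|---|
| 10% | 55.7% | 10.6 | 60.1% | 9.5 |
| 20% | 52.8% | 11.3 | 62.2% | 9.0 |
| 30% | 49.0% | 12.1 | 64.3% | 8.5 |
| 40% | 44.0% | 13.3 | 66.4% | 8.0 |

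Against the anticipated 10 points, the shift is 0.5 to 3.3 points. With 10 discordant patients in 100, all SSS-positive and CH-negative, the half-width of the paired difference is 1.96·√(0.1·0.9/100) = 5.9 points.

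**6. Cross-check with another model.** Assume exclusive tonsil and tongue-base prevalences of 25% and 43%, CH sensitivity 0.853 and SSS sensitivity 1. This returns 58% and 68% with nobody staged. At 50% staged, CH is 52.3% and the difference 11.4 points, the same directions as reading A.

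**7. Counted per specimen.** Adding m earlier tonsils with SSS yield q to N specimens with CH rate r and difference d gives CH = rN/(N+m) and difference (dN+qm)/(N+m). CH falls, but the difference rises only if q > d.

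**The case against.** The strongest reply is that pooling is the stated primary question. The objective covers TBM and tonsil tissue, and the aim is to describe current UK management, staged patients included. Each specimen has both a CH and an SSS result, so the contrast is paired and valid whatever the mix. That stands. A reader might infer that pooling biases or invalidates the primary comparison. The documents do not support this: case mix affects how the difference generalises, and the illustrated shift is smaller than sampling error.

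It can also be said that 12.4 does not forbid further breakdowns, that such rows are usual SAP content, and that the CRF or local histopathology reports may already show tonsil timing. That stands too, and it makes the split by timing an improvement rather than the correction of an error. It does not reach the endpoint of secondary objective 1, which the protocol itself fixes in conflict with its objective.

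Finally, a reader might infer that a TBM-only endpoint removes confounding by staging. It does not, as step 4 shows. No section links staging to surgical method, and the 25% and 75% shares are arbitrary. The case for restriction is the wording of the objective alone.

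**Conclusion.** The endpoint of secondary objective 1 is wrong as written: 6.3 asks about TBM specimens and 12.2 adds tonsils. This rests on the text and needs no assumption. How much the tonsils add is not known; under the assumptions of step 3 it is (1-s)t.

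The point about earlier tonsils also holds, as a cheap improvement. Their CH-negativity follows from 8.3, but only for tonsils reported before TBM was indicated; tonsils taken with the TBM are unaffected. Its effect on the pooled difference, 0.5 to 3.3 points at a 50% staged share, depends on assumed tonsil rates, an assumed share, and a yield g that is the same in staged and unstaged patients. It bears on interpretation and is not a large bias. The pooled CH rate, the pooled SSS rate and their paired difference should be kept.

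**What to change.** 1. In 12.2, and in the surgical-method rates of 12.4, restrict the endpoint for secondary objective 1 to cancer identified in the TBM specimen. This is a change of wording and needs no new data.
2. Show the method comparison separately for patients whose tonsils were already reported negative before TBM was indicated and for the others. If numbers are too small, give at least the staged share for each method.
3. Keep the pooled rates and the paired difference in 12.4. Beside them report CH and SSS rates for TBM specimens and for tonsils not reported before the TBM indication. For earlier CH-negative tonsils report only the SSS added yield, since their CH rate is zero by selection.
4. Record for each tonsil whether it was reported before TBM was indicated, if this cannot be recovered from the surgical history or the local reports.

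The cost is a few descriptive rows, at most one timing item per tonsil, and smaller strata. At a yield of 23.8%, the 95% half-width 1.96·√(g(1-g)/n) is about 12.9 points with 42 CH-negative patients and 18.2 points with 21, so the added rows should be read as descriptive.
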